7.7. Concomitant Therapy

Any medication or vaccine (including over-the-counter or prescription medicines, vitamins, and/or herbal supplements) that the participant is receiving at the time of enrolment or receives during the study must be recorded along with:

- reason for use
- dates of administration including start and end dates
- dosage information including dose and frequency

The Medical Monitor should be contacted if there are any questions regarding concomitant or prior therapy.

Participants must abstain from taking prescription or non-prescription drugs (including vitamins and dietary or herbal supplements) within 7 days (or 14 days if the drug is a

potential enzyme inducer) or 5 half-lives (whichever is longer) before the start of study treatment until completion of the follow-up visit, unless, in the opinion of the investigator and sponsor, the medication will not interfere with the study.

Paracetamol, at doses of ≤ 2 grams/day, is permitted for use any time during the study. Other concomitant medication may be considered on a case-by-case basis by the investigator in consultation with the Medical Monitor if required.

7.8. Treatment after the End of the Study

This is a study in healthy participants who will not receive any treatment after the end of the study.

8. DISCONTINUATION CRITERIA

8.1. Discontinuation of Study Treatment

Participants will be permanently withdrawn from study treatment, at the discretion of the investigator after receiving the first dose of study medication.

[figure not shown]
8.1.1. Liver Chemistry Stopping Criteria

Liver chemistry stopping and increased monitoring criteria have been designed to assure participant safety and evaluate liver event etiology.

Discontinuation of study treatment for abnormal liver tests is required when a participant meet one of the conditions outlined in [Figure 2](#) below or if the investigator believes that it is in the best interest of the participant.

Study treatment will be discontinued **for a participant** if liver chemistry stopping criteria are met:

Figure 2 Phase I Liver Chemistry Stopping Criteria – Liver Stopping Event Algorithm

Liver Safety Required Actions and Follow up Assessments Section can be found in [Appendix 6](#).

8.1.2. QTc Stopping Criteria

- The *same* QT correction formula *must* be used for *each individual participant* to determine eligibility for and discontinuation from the study. This formula may not be changed or substituted once the participant has been enrolled.
 - For example, if a participant is eligible for the protocol based on QTcB, then QTcB must be used for discontinuation of this individual participant as well.
 - Once the QT correction formula has been chosen for a participant's eligibility, the *same formula* must continue to be used for that participant *for all QTc data being collected for data analysis*. Safety ECGs and other non-protocol specified ECGs are an exception.
- The QTcB should be based on single QTcB values obtained over a brief (e.g., 5-10 minute) recording period.

A participant that meets either of the bulleted criteria below will be withdrawn from study treatment.

- QTc, QTcB, >500 msec,
- Change from baseline: QTc >60 msec

See the SoA for data to be collected at the time of treatment discontinuation and follow-up and for any further evaluations that need to be completed.

8.1.3. Temporary Discontinuation

Participants withdrawn from study treatment, will continue in the study until completion of their follow up visit for the study period.

8.2. Withdrawal from the Study

- A participant may withdraw from the study at any time at his/her own request, or may be withdrawn at any time at the discretion of the investigator for safety, behavioral, compliance or administrative reasons.
- If the participant withdraws consent for disclosure of future information, the sponsor may retain and continue to use any data collected before such a withdrawal of consent.
- If a participant withdraws from the study, he/she may request destruction of any samples taken and not tested, and the investigator must document this in the site study records.
- Refer to the SoA for data to be collected at the time of study discontinuation and follow-up and for any further evaluations that need to be completed.

8.3. Lost to Follow Up

A participant will be considered lost to follow-up if he or she repeatedly fails to return for scheduled visits and is unable to be contacted by the study site.

The following actions must be taken if a participant fail to return to the clinic for a required study visit:

- The site must attempt to contact the participant and reschedule the missed visit as soon as possible and counsel the participant on the importance of maintaining the assigned visit schedule and ascertain whether or not the participant wishes to and/or should continue in the study.
- Before a participant is deemed lost to follow up, the investigator or designee must make every effort to regain contact with the participant (where possible, three (3) telephone calls and, if necessary, a certified letter to the participant's last known mailing address or local equivalent methods). These contact attempts should be documented in the participant's medical record.
- Should the participant continue to be unreachable, he/she will be considered to have withdrawn from the study with a primary reason of lost to follow-up.

9. STUDY ASSESSMENTS AND PROCEDURES

Study procedures and their timing are summarized in the SoA.

- Protocol waivers or exemptions are not allowed

- Immediate safety concerns should be discussed with the sponsor immediately upon occurrence or awareness to determine if the participant should continue or discontinue study treatment.
- Adherence to the study design requirements, including those specified in the SoA, is essential and required for study conduct.
- All screening evaluations must be completed and reviewed to confirm that potential participants meet all eligibility criteria. The investigator will maintain a screening log to record details of all participants screened and to confirm eligibility or record reasons for screening failure, as applicable.
- During screening the following will be completed:
 - Demographic parameters will be captured: Year of birth, sex, race and ethnicity.
 - Medical /Medication /family history will be assessed as related to the inclusion/exclusion criteria in Section 6.
- Procedures conducted as part of the participant's routine clinical management (eg, blood count) and obtained before signing of ICF may be utilized for screening or baseline purposes provided the procedure met the protocol-specified criteria and was performed within the time frame defined in the SoA.
- Blood samples will be collected as per SoA.
 - The maximum amount of blood collected from each participant over the duration of the study, including any extra assessments that may be required, will not exceed 500 mL.
 - Repeat or unscheduled samples may be taken for safety reasons or for technical issues with the samples.

9.1. Efficacy Assessments

Not applicable

9.2. Adverse Events

The definitions of an AE or SAE can be found in [Appendix 4](#).

The investigator and any designees are responsible for detecting, documenting, and reporting events that meet the definition of an AE or SAE and remain responsible for following up AEs that are serious, considered related to the study treatment or the study, or that caused the participant to discontinue the study treatment/study (see Section 8).

9.2.1. Time Period and Frequency for Collecting AE and SAE Information

- All SAEs will be collected from the time a participant consents to participate in the study until the follow-up visit at the time points specified in the SoA (Section 2).

- All AEs will be collected from the start of IP administration until the follow-up contact at the time points specified in the SoA (Section 2).
- Medical occurrences that begin before the start of study treatment but after obtaining informed consent will be recorded on the Medical History/Current Medical Conditions section of the case report form (CRF) not the AE section.
- All SAEs will be recorded and reported to the sponsor or designee immediately and under no circumstance should this exceed 24 hours, as indicated in [Appendix 4](#). The investigator will submit any updated SAE data to the sponsor within 24 hours of it being available.
- Investigators are not obligated to actively seek AEs or SAEs in former study participants. However, if the investigator learns of any SAE, including a death, at any time after a participant has been discharged from the study, and he/she considers the event to be reasonably related to the study treatment or study participation, the investigator must promptly notify the sponsor.
- The method of recording, evaluating, and assessing causality of AEs and SAEs and the procedures for completing and transmitting SAE reports are provided in [Appendix 4](#).

9.2.2. Method of Detecting AEs and SAEs

Care will be taken not to introduce bias when detecting AE and/or SAE. Open-ended and non-leading verbal questioning of the participant is the preferred method to inquire about AE occurrence.

9.2.3. Follow-up of AEs and SAEs

After the initial AE/SAE report, the investigator is required to proactively follow each participant at subsequent visits/contacts. All SAEs and non-serious AEs will be followed until the event is resolved, stabilized, otherwise explained, or the participant is lost to follow-up (as defined in Section 8.3). Further information on follow-up procedures is given in [Appendix 4](#).

9.2.4. Regulatory Reporting Requirements for SAEs

- Prompt notification by the investigator to the sponsor of a SAE is essential so that legal obligations and ethical responsibilities towards the safety of participants and the safety of a study treatment under clinical investigation are met.
- The sponsor has a legal responsibility to notify both the local regulatory authority and other regulatory agencies about the safety of a study treatment under clinical investigation. The sponsor will comply with country-specific regulatory requirements relating to safety reporting to the regulatory authority, Institutional Review Boards (IRB)/Independent Ethics Committees (IEC), and investigators.

- Investigator safety reports must be prepared for suspected unexpected serious adverse reactions (SUSAR) according to local regulatory requirements and sponsor policy and forwarded to investigators as necessary.
- An investigator who receives an investigator safety report describing a SAE or other specific safety information (eg, summary or listing of SAE) from the sponsor will review and then file it along with the Investigator's Brochure and will notify the IRB/IEC, if appropriate according to local requirements.

9.2.5. Pregnancy

- Details of all pregnancies in female participants and, if indicated, female partners of male participants will be collected from the start of study treatment until 5 days after the last dose or until the follow up visit where indicated.
- If a pregnancy is reported, the investigator should inform GSK within 24 hrs of learning of the pregnancy and should follow the procedures outlined in [Appendix 5](#)
- Abnormal pregnancy outcomes (eg, spontaneous abortion, fetal death, stillbirth, congenital anomalies, ectopic pregnancy) are considered to be a SAE.

9.3. Treatment of Overdose

For this study, any dose of SKF101804 or reference greater than 200 mg/ 5 mL within a 24-hour time period will be considered an overdose.

In the event of acute excessive oral over dosage, routine emergency measures must be followed. In addition, ECG, renal function and urine pH should be monitored. Administer magnesium or calcium containing antacids which reduce the absorption of cefixime. Adequate hydration must be maintained. The administration of activated charcoal as soon as possible after oral overdose may prevent excessive increase of systemic cefixime exposure. The principal investigator will be responsible for the appropriate medical management of any participant who has an overdose.

In the event of an overdose, the investigator/treating physician should:

1. Contact the Medical Monitor immediately.
2. Closely monitor the participant for AE/SAE and laboratory abnormalities until cefixime can no longer be detected systemically (at least 3 days).
3. Obtain a plasma sample for PK analysis within 3 days from the date of the last dose of study treatment if requested by the Medical Monitor (determined on a case-by-case basis).
4. Document the quantity of the excess dose as well as the duration of the overdosing in the CRF.

Decisions regarding dose interruptions or modifications will be made by the investigator in consultation with the Medical Monitor based on the clinical evaluation of the participant.

9.4. Safety Assessments

Planned time points for all safety assessments are provided in the SoA.

Additional time points for safety tests (such as vital signs, physical exams and laboratory safety tests) may be added during the course of the study based on newly available data or investigator's discretion to ensure appropriate safety monitoring.

9.4.1. Physical Examinations

- A complete physical examination will include, at a minimum, assessments of the Skin, Cardiovascular, Respiratory, Gastrointestinal and Neurological systems. Height and weight will also be measured and recorded.
- A brief physical examination will include, at a minimum, assessments of the skin, lungs, cardiovascular system, and abdomen (liver and spleen).
- Investigators should pay special attention to clinical signs related to previous serious illnesses.

9.4.2. Vital Signs

- Temperature, pulse rate, respiratory rate, and blood pressure will be assessed.
- Blood pressure and pulse measurements will be assessed in a supine position with a completely automated device. Manual techniques will be used only if an automated device is not available.
- Blood pressure and pulse measurements should be preceded by at least 5 minutes of rest for the participant in a quiet setting without distractions (eg, television, cell phones).
- Vital signs will be measured in a supine position after 5 minutes rest and will include temperature, systolic and diastolic blood pressure, and pulse.

9.4.3. Electrocardiograms

- Single 12-lead ECGs will be obtained as outlined in the SoA using an ECG machine that automatically calculates the heart rate and measures PR, QRS, QT, and QTc intervals. Refer to Section 8.1.2 for QTc withdrawal criteria and additional QTc readings that may be necessary.
- ECGs will be measured in a supine position after 5 minutes rest.

9.4.4. Clinical Safety Laboratory Assessments

- Refer to [Appendix 2](#) for the list of clinical laboratory tests to be performed and to the SoA for the timing and frequency.
- The investigator must review the laboratory results, document this review, and record any clinically relevant changes occurring during the study in the AE

section of the CRF or equivalent. Clinically significant abnormal laboratory findings are those which are not usually expected for a healthy participant.

- All laboratory tests with values considered clinically significantly abnormal during participation in the study or within 7 days after the last dose of study treatment should be repeated until the values return to normal or baseline or are no longer considered significantly abnormal by the investigator or medical monitor.
- If such values do not return to normal/baseline within a period of time judged reasonable by the investigator, the etiology should be identified and the sponsor notified.
- All protocol-required laboratory assessments, as defined in [Appendix 2](#), must be conducted in accordance with the PAREXEL laboratory manual, PAREXEL standard operating procedure (SOPs) and the SoA.
- Refer to the PAREXEL SOPs for appropriate processing and handling of samples to avoid duplicate/ and or additional blood draws.

9.5. Pharmacokinetics

- Venous blood samples, 4 mL each, for the determination of cefixime plasma concentrations will be collected in lithium heparin tubes. The actual date and time (24-hour clock time) of each sample will be recorded.
- Blood samples will be placed on ice between sample collection and centrifuging. Within one hour of collection, blood samples will be centrifuged at approximately 2700 g within a range of 0°C to 8°C for 10 minutes. Thereafter, the supernatant of each sample will be divided into 2 aliquots (of at least 0.8 mL plasma each, transferred to labeled, plastic tubes and frozen (- 20°C).
- Plasma samples will be stored at approximately -20°C in a temperature monitored freezer until transfer to PAREXEL Bioanalytical Services Division (BASD). Pooled samples for concentration range estimation will be prepared according to PAREXEL standard operating procedures (SOPs).
- Unused duplicate plasma PK samples will be stored at BASD for 6 months after completion of the bioanalysis phase of the study. The sponsor will be required to indicate whether additional storage is needed or whether the samples may be discarded.
- Samples collected for analyses of cefixime concentration may also be used to evaluate safety or efficacy aspects related to concerns arising during or after the study.
- A validated bioanalytical method, as described in the PAREXEL bioanalytical protocol will be used for quantitative analysis.

9.6. Pharmacodynamics

Pharmacodynamic parameters are not evaluated in this study.

9.7. Genetics

Genetics are not evaluated in this study.

9.8. Biomarkers

Biomarkers are not evaluated in this study.

9.9. Health Economics OR Medical Resource Utilization and Health Economics

Health Economics/Medical Resource Utilization and Health Economics parameters are not evaluated in this study.

10. STATISTICAL CONSIDERATIONS

Refer to Analysis Plan ([Appendix 7](#)).

Bioequivalence

The primary objective of this study is to demonstrate BE between the test 200 mg/5 mL suspension formulation SKF101804 and the reference formulation, based on PK endpoints C_{\max} and $AUC_{(0-t)}$ of cefixime.

The null hypothesis is that the true ratio of the geometric mean of the test treatment to the geometric mean of the reference treatment, $\mu_{(\text{Test})}/\mu_{(\text{Reference})}$, for the C_{\max} , or $AUC_{(0-t)}$, is either <0.80 or >1.25 for plasma cefixime.

The alternate hypothesis is that the true ratio of the geometric mean of the test treatment to the geometric mean of the reference treatment for both the C_{\max} , and $AUC_{(0-t)}$, is ≥ 0.80 and ≤ 1.25 for plasma cefixime.

Symbolically this is expressed as follows:

$$H_0: \mu_{(\text{Test})}/\mu_{(\text{Reference})} < 0.80 \text{ or } \mu_{(\text{Test})}/\mu_{(\text{Reference})} > 1.25$$

i.e., treatments are not bioequivalent.

versus

$$H_a: 0.80 \leq \mu_{(\text{Test})}/\mu_{(\text{Reference})} \leq 1.25$$

i.e., treatments are bioequivalent.

For each PK parameter designated as a primary endpoint, a two one-sided t-test (TOST)[[Schuirmann, 1987](#)] procedure with $\alpha=0.05$ for each one-sided test will be used to test this set of hypotheses. Bioequivalence will be declared if the 90% CI for the true ratio of test to reference geometric means falls entirely within the range of 0.80 to 1.25 for all primary parameters.

For BE to be declared, the null hypothesis must be rejected, for all primary parameters C_{max} , and $AUC_{(0-t)}$, for cefixime.

10.1. Sample Size Determination

Sample Size Rationale:

Bioequivalence is to be determined on the basis of the primary endpoints C_{max} and $AUC_{(0-t)}$ of cefixime.

Intra participant coefficient of variation (CV_w) estimates in recent published data for cefixime with highest CV% was reported as approximately 19.5% for C_{max} of cefixime [Asiri, 2005].

Hence, the sample size for this trial was determined based on maximum observed intra participant CV of 19.5%.

Based on a BE range of 80.00% to 125.00% for C_{max} and $AUC_{(0-t)}$, for cefixime assuming intra participant CV to be 20% and a "test/reference" mean ratio of 0.95; 24 evaluable participants are needed to achieve a power of 90% at an alpha level of 0.05 for the single test for testing BE.

Approximately 28 eligible participants (assuming approximately 15% drop out rate) will be entered into the study to complete the study with at least 24 evaluable participants. See Section 5.2

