5. STUDY DESIGN

5.1. Overall Design

This is a Phase I, open label, balanced, randomised, single dose, two-way crossover study, enrolling approximately 28 healthy participants at a single centre.

Each enrolled study participant will participate in two treatment periods in accordance with the randomisation schedule. Treatment period 2 will be separated by a washout period of at least 7 days and no more than 14 days from Treatment Period 1, Day 2.

Figure 1 Study Schematic

Study participants will be randomised to one of two treatment sequences (A-B or B-A). A single dose of one of the two treatments A or B, will be administered on Day 1, in each treatment period. Each participant will participate in both treatment periods and receive a single dose of each treatment.

Study treatments will be referred to as Test and Reference throughout the protocol:

- **Treatment A – Test: SKF101804 (FIXVAL™)** 200 mg cefixime (200 mg/5 mL powder for suspension).
- **Treatment B - Reference: (Cefspan),** 200 mg cefixime (200 mg/5 mL powder for suspension).

Treatment periods 1 and 2 will be separated by a washout period of 7 to 14 days.

The total duration in the study for each participant is expected to be 5 to 7 weeks, from screening to their last visit.

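### Does the 90% power in Section 10.1 fail, either at the stated CV or because both endpoints must pass?

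*Combined protocol and SAP*

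**What the plan says.** Section 10.1 (Sample Size Determination) takes its variability from published cefixime data, "with highest CV% was reported as approximately 19.5% for C_{max} of cefixime", and states that "the sample size for this trial was determined based on maximum observed intra participant CV of 19.5" percent. The next paragraph plans with a CV of 20%, a true ratio of 0.95 and limits of 80.00% to 125.00%, and concludes that "24 evaluable participants are needed to achieve a power of 90% at an alpha level of 0.05 for the single test for testing BE". About 28 are entered so that at least 24 are evaluable. Section 5.2 uses that required number to decide whether withdrawn participants are replaced.

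The decision rule is in Section 10: "For BE to be declared, the null hypothesis must be rejected, for all primary parameters", namely Cmax and AUC(0-t). Each endpoint is tested by two one-sided tests at 0.05, which is equivalent to using a 90% confidence interval. Section 5.1 describes a "balanced, randomised, single dose, two-way crossover study".

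**The concern.** Two things look wrong on a first reading. The section names two CVs, and the choice between them decides which side of 90% the power falls on with 24 participants. Taken strictly at 20%, 24 falls just short, and the smallest balanced number that reaches 90% is 26.

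The second matters more. The power is quoted for one test, but the trial succeeds only if two tests succeed. Unless the endpoints are perfectly correlated, or one of them is almost certain to pass, the chance of success is below the single-test figure. A sponsor who took 90% as the chance of success would understate the risk of a failed study for a product that is truly equivalent. Because 24 is also the replacement threshold, the trial may properly finish at the number where that risk is highest.

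**Working it through.** **Inputs from the documents.** Ratio 0.95, limits 0.80 and 1.25, CV 20% (source value 19.5%), and 24 evaluable (Section 10.1); one-sided alpha 0.05 and the both-endpoints rule (Section 10); balanced two-period crossover (Section 5.1), so residual df = n − 2 = 22.

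**Assumed, because the documents do not give them.** The correlation between the Cmax and AUC(0-t) treatment differences, and a separate CV for AUC(0-t).

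**Step 1: reproduce the single-test power at CV 20%.**
- Log-scale SD: s = √ln(1 + 0.20²) = 0.1980.
- Standard error of the treatment difference: s × √(2/24) = 0.1980 × 0.2887 = 0.0572.
- Distance from ln 0.95 to ln 0.80: 0.1719, or 3.01 standard errors. Distance to ln 1.25: 0.2744, or 4.80 standard errors.
- Critical value t(0.95, 22) = 1.717.
- Exact power, integrating over the distribution of the residual variance: **89.6%**. The normal approximation gives 91.2%, and the shifted central-t approximation gives 89.2%.

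**Step 2: repeat at CV 19.5%.** s = 0.1932, SE = 0.0558, distance to the lower limit 3.08 standard errors, exact power **90.9%**. The CV at which 24 participants give exactly 90% is 19.85%, between the two values in the section.

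**Step 3: strict sample size at CV 20%.** Exact power is 90.7% with 25 and 91.8% with 26. The strict balanced answer is therefore 26, two more than planned and within the 28 entered.

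**Step 4: power to pass both endpoints with 24 evaluable, both ratios 0.95** (simulation with correlated differences and a Wishart residual covariance):

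| Cmax CV | AUC CV | Correlation | Power for both |
|---|---|---|---|
| 20% | 20% | 0 | about 80% (0.896 × 0.896 = 0.803) |
| 20% | 20% | 0.5 | 82.5% |
| 20% | 20% | 0.8 | about 85% |
| 20% | 20% | 0.9 | 86.3% |
| 20% | 20% | 0.95 | 87.2% |
| 20% | 20% | 1 | 89.6% |
| 20% | 18% | 0 to 0.8 | 84.5 to 87.8% |
| 20% | 15% | 0 to 0.8 | 88.4 to 89.5% |
| 20% | 12% or less | 0 to 0.8 | about 89.5% |

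An AUC CV of 15% gives almost the single-test value because AUC alone then passes with 98.7% power: 0.896 × 0.987 = 0.884 even at zero correlation.

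**Step 5: if all 28 are evaluable.** Single-test power at CV 20% is 93.5%. With both CVs at 20%, power for both endpoints is 87.4% at correlation 0 (0.935 × 0.935 = 0.874) and about 91.2% at 0.9.

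**The case for a change.** The strongest case for acting is that the only power figure in the plan does not answer the question a sponsor cares about. Section 10.1 itself opens by resting bioequivalence on both endpoints, and it applies one CV and one ratio to both. Taken literally, those inputs give 80 to 86% over correlations of 0 to 0.9, a failure risk of roughly 14 to 20% rather than 10%. Section 5.4 calls the study pivotal, and a few added sentences would cost nothing.

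Part of this stands. The joint power is not stated, and with equal CVs of 20% it is below 89.6% for any correlation short of 1. The sentence that ties the size to 19.5% is also loosely drafted.

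The rest is weaker. The plan says plainly that its figure is for a single test, and Section 10 states the both-endpoints rule openly, so no false claim is made. The 20% comes from the highest CV found, which was for Cmax. Using it for AUC as well is a cautious ceiling and not a forecast of AUC variability. The 80% end needs two parameters from the same concentration profile to be uncorrelated, and the 86% end is an arbitrary stop at 0.9. All of these figures also assume the minimum of 24, while 28 are entered.

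**Conclusion.** The concern does not hold as an error. The 90% for one test is reproduced: 89.6% at CV 20% and 90.9% at CV 19.5%, both within one percentage point of the stated figure. Reading 20% as the approximate 19.5% rounded up explains why two values appear, and 24 fits either of them.

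For the both-endpoints decision, power at 24 evaluable and ratio 0.95 is about 80 to 90%. It is 80 to 86% only if both CVs are 20% and the correlation lies between 0 and 0.9. It is about 88 to 90% if the AUC CV is 15%. With all 28 evaluable and both CVs at 20%, it is about 87 to 91% over the same correlations. The correlation and the AUC CV are assumptions, so no single joint figure follows from the documents.

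What remains is a supplementary figure that a statistician can derive from the stated inputs once a correlation and an AUC CV are assumed. Stating it would not alter enrolment, the replacement threshold, the model, the error rate or the way bioequivalence is declared. Requiring both endpoints to pass does not inflate the type I error, so only the sponsor's risk of an unsuccessful study is affected. No change to the plan follows.
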